#### 10.2.1. Functional Assessment of Cancer Therapy—Head and Neck (FACT-H&N) Instrument

The FACT-H&N is a multidimensional, self-report quality of life instrument specifically designed for use with head and neck cancer patients. It consists of 28 core items, the FACT-G, which assess patient function in four domains: Physical, Social/Family, Emotional, Functional well-being, and relationship with doctor which is further supplemented by 12 head and neck-specific items to assess head and neck related symptoms, and form the FACT-Head and Neck Subscale (HNS). Each item is rated on a 0 to 4 Likert type scale, and then combined to produce subscale scores for each domain, as well as a global QoL score. Higher scores represent better quality of life.

Ten items of the FACT-H&N also form a symptom related index, FHNSI-10, which can be analyzed separately.

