**FACT-H&N (Version 4)**

Below is a list of statements that other people with your illness have said are important. Please circle or mark one number per line to indicate your response as it applies to the past 7 days.

PHYSICAL WELL-BEING		Not at all	A little bit	Some-what	Quite a bit	Very much
QP1	I have a lack of energy .....	0	1	2	3	4
QP2	I have nausea .....	0	1	2	3	4
QP3	Because of my physical condition, I have trouble meeting the needs of my family .....	0	1	2	3	4
QP4	I have pain .....	0	1	2	3	4
QP5	I am bothered by side effects of treatment .....	0	1	2	3	4
QP6	I feel ill .....	0	1	2	3	4
QP7	I am forced to spend time in bed .....	0	1	2	3	4

SOCIAL/FAMILY WELL-BEING		Not at all	A little bit	Some-what	Quite a bit	Very much
QS1	I feel close to my friends .....	0	1	2	3	4
QS2	I get emotional support from my family .....	0	1	2	3	4
QS3	I get support from my friends .....	0	1	2	3	4
QS4	My family has accepted my illness .....	0	1	2	3	4
QS5	I am satisfied with family communication about my illness .....	0	1	2	3	4
QS6	I feel close to my partner (or the person who is my main support) .....	0	1	2	3	4
Q1	Regardless of your current level of sexual activity, please answer the following question. If you prefer not to answer it, please mark this box  and go to the next section.					
QS7	I am satisfied with my sex life .....	0	1	2	3	4

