**FACT-H&N (Version 4)**

Please circle or mark one number per line to indicate your response as it applies to the past 7 days.

EMOTIONAL WELL-BEING		Not at all	A little bit	Some-what	Quite a bit	Very much
OE1	I feel sad .....	0	1	2	3	4
OE2	I am satisfied with how I am coping with my illness .....	0	1	2	3	4
OE3	I am losing hope in the fight against my illness .....	0	1	2	3	4
OE4	I feel nervous .....	0	1	2	3	4
OE5	I worry about dying .....	0	1	2	3	4
OE6	I worry that my condition will get worse .....	0	1	2	3	4

FUNCTIONAL WELL-BEING		Not at all	A little bit	Some-what	Quite a bit	Very much
OF1	I am able to work (include work at home) .....	0	1	2	3	4
OF2	My work (include work at home) is fulfilling .....	0	1	2	3	4
OF3	I am able to enjoy life .....	0	1	2	3	4
OF4	I have accepted my illness .....	0	1	2	3	4
OF5	I am sleeping well .....	0	1	2	3	4
OF6	I am enjoying the things I usually do for fun .....	0	1	2	3	4
OF7	I am content with the quality of my life right now .....	0	1	2	3	4

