**FACT-H&N (Version 4)**

Please circle or mark one number per line to indicate your response as it applies to the past 7 days.

ADDITIONAL CONCERNS		Not at all	A little bit	Some- what	Quite a bit	Very much
H&N1	I am able to eat the foods that I like .....	0	1	2	3	4
H&N2	My mouth is dry .....	0	1	2	3	4
H&N3	I have trouble breathing .....	0	1	2	3	4
H&N4	My voice has its usual quality and strength .....	0	1	2	3	4
H&N5	I am able to eat as much food as I want .....	0	1	2	3	4
H&N6	I am unhappy with how my face and neck look.....	0	1	2	3	4
H&N7	I can swallow naturally and easily .....	0	1	2	3	4
H&N8	I smoke cigarettes or other tobacco products .....	0	1	2	3	4
H&N9	I drink alcohol (e.g. beer, wine, etc.).....	0	1	2	3	4
H&N 10	I am able to communicate with others .....	0	1	2	3	4
H&N 11	I can eat solid foods.....	0	1	2	3	4
H&N 12	I have pain in my mouth, throat or neck .....	0	1	2	3	4

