5.6.2. Patient Reported Outcomes

Patient-reported outcomes will be used to evaluate study treatment in subjects treated with patritumab + cetuximab + platinum-based therapy compared to placebo + cetuximab + platinum-based therapy.

Functional Assessment of Cancer Therapy—Head and Neck (FACT-H&N) Instrument

The FACT-H&N contains 4 general subscales (total 27 items) measuring physical well-being (PWB), functional well-being (FWB), social well-being (SWB), emotional well-being (EWB), and a Head and Neck Cancer symptom-specific subscale – the 12-item Head and Neck Additional Concerns Subscale (HNS). Each of the 39 FACT-H&N items is rated on 5-point scales, ranging from 0=not at all to 4=very much, where higher scores represent more favorable patient-reported outcomes.

Combining the 10 symptom-related items out of the 39 FACT-H&N items – “I have a lack of energy” (PWB item 1), “I have nausea” (PWB item 2), “I have pain” (PWB item 4), “I worry that my condition will get worse” (EWB item 6), “I am content with the quality of my life right now” (FWB item 7), “I have trouble breathing” (Additional Concerns item 3), “I can swallow naturally and easily” (Additional Concerns item 7), “I am able to communicate with others” (Additional Concerns item 10), “I can eat solid foods” (Additional Concerns item 11), and “I have pain in my mouth, throat or neck” (Additional Concerns item 12) - yields a 10-item FACT-Head and Neck Symptom Index (FHNSI).

Specifically, 7 specific summary scores will be evaluated,

- PWB score
- FWB score
- SWB score
- EWB score
- HNS score
- FHNSI score
- FACT-H&N total score

The FACT-H&N Total Score ranges from 0-156. The PWB score, SWB score and EWB score range from 0 to 28. The EWB score ranges from 0 to 24. The HNS score and the FHNSI score ranges from 0 to 48. The FACT-H&N total score, PWB score, FWB score,

SWB score, EWB score, HNS score and FHNSI score will be analyzed as exploratory efficacy parameters.

Use following algorithm to determine the individual subscale scores:

- Physical well-being (PWB): PWB score = $\text{Sum (GP1-GP7)} \times 7 / \text{number of nonmissing items}$. If the number of missing items (GP1-GP7) is greater than 3, then set PWB score = missing.
- Social well-being (SWB): SWB score = $\text{Sum (GS1-GS7)} \times 7 / \text{number of nonmissing items}$. If the number of missing items (GS1-GS7) is greater than 3, then set SWB score = missing.

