- Emotional well-being (EWB): EWB score = $\text{Sum (GE1-GE6)} \times 6 / \text{number of nonmissing items}$. If the number of missing items (GE1-GE6) is greater than 3, then set EWB score = missing.
- Functional well-being (FWB): FWB score = $\text{Sum (GF1-GF7)} \times 7 / \text{number of nonmissing items}$. If the number of missing items (GF1-GF7) is greater than 3, then set FWB score = missing.
- Additional Concern (HNS): HCS score = $\text{Sum (H\&N1-H\&N12)} \times 12 / \text{number of nonmissing items}$. If the number of missing above items is greater than 6, then set HCS score = missing.
- Additional Concern (HNS): HCS score = $\text{Sum (H\&N1-H\&N12)} \times 12 / \text{number of nonmissing items}$. If the number of missing above items is greater than 6, then set HCS score = missing.
- FHNSI: FHNSI score = $\text{Sum of 10 symptom-related items} \times 10 / \text{number of nonmissing items}$. If the number of missing above items is greater than 5, then set FHNSI score = missing.
- FACT-H&N total score: FACT-H&N score = $\text{Sum (PWB, SWB, EWB, GFB, HCS)}$. If any of the above items is missing, then set FACT-H&N score = missing.

EuroQoL-5 Dimensions-5 Levels Instrument

The EQ-5D-5L is a preference based measure of health status that is now widely used in clinical trials, observational studies, and other health surveys.

The EQ-5D-5L consists of 2 pages – the EQ-5D-5L descriptive system and the EuroQoL Visual Analogue scale (EQ VAS). The descriptive system comprises the following 5 domains: mobility, self-care, usual activities, pain/discomfort, anxiety/depression. Each domain has 5 levels: no problems (1), slight problems (2), moderate problems (3), severe problems (4), and extreme problems (5). The respondent is asked to indicate his/her health state by ticking (or placing a cross) in the box with the most appropriate statement in each of the 5 domains. This decision results in a 1-digit number expressing the level selected for that domain. The digits for 5 domains can be combined in a 5-digit number or profile describing the respondent's health state.

As index-based values have not been evaluated for the EQ-5D-5L at this time, crosswalk value sets developed based on the EQ-5D-3L index-based values will be applied. The crosswalk value set for the United Kingdom will be used for analyses overall and for all regions. The value set provides an index score for each health state and can be accessed at:

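### SAP 5.6.2 sums FACT-H&N items without reversing the 16 negatively worded ones: PWB is inverted, EWB and FHNSI are net inverted, and HNS, FACT-G and the total are distorted

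*SAP*

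**What the plan says.** SAP 5.6.2 puts all 39 FACT-H&N items on one five-point agreement scale, "ranging from 0=not at all to 4=very much, where higher scores represent more favorable patient-reported outcomes". Protocol 10.2.1 gives the scores the same direction: "Higher scores represent better quality of life".

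SAP 5.6.2 then sets out its own algorithm. PWB, SWB, EWB, FWB and HNS are each the sum of their items, multiplied by the number of items and divided by the number answered. FHNSI is built the same way from the "Sum of 10 symptom-related items". The FACT-H&N total is the sum of the five subscales. Rules for missing items are given. No item is recoded.

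The questionnaire in Protocol Appendix 17.2.1 includes items such as "I am bothered by side effects of treatment", "I worry about dying" and "I have pain in my mouth, throat or neck", answered on the same 0 to 4 scale as the favourable items.

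The ranges in SAP 5.6.2 are also unsound. For the well-being subscales it says "The PWB score, SWB score and EWB score range from 0 to 28. The EWB score ranges from 0 to 24", and for the symptom scores "The HNS score and the FHNSI score ranges from 0 to 48".

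**The concern.** The stated direction and the stated sums cannot both hold. If the raw answers are added, a patient with severe nausea, pain and side effects gets a high PWB score, which the plan reads as good.

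Five of the seven summary scores listed in SAP 5.6.2 are affected (PWB, EWB, HNS, FHNSI and the total), as is the FACT-G total added in SAP 8.7.1. The errors carry into these planned outputs:

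- The by-visit summaries and mixed models in SAP 8.7.1.
- All three scores that SAP 8.7.1 names for the cumulative distribution plots (FACT-G, FHNSI, total), and HNS, which is what the Figure 15.5.1.1 shell plots instead.
- One of the eleven exploratory PFS and OS subgroup factors in SAP 8.2.4.2, which splits the baseline total at its median.

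The direction matters in this trial. Protocol 1.3 lists diarrhea and vomiting among the most significant reactions to patritumab, and the fully inverted domain holds the nausea and side-effect items. The mixed-model contrast could show the more toxic arm as better.

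**Working it through.** **Inputs.** Item wording comes from Protocol Appendix 17.2.1. The formulas and the list of FHNSI items come from SAP 5.6.2. Call an item positive if agreement is favourable and negative if it is unfavourable.

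- PWB: 7 of 7 negative.
- SWB and FWB: 0 of 7 negative in each, so both are correct as written.
- EWB: 5 of 6 negative (all but GE2).
- H&N: 4 of 12 clearly negative (items 2, 3, 6, 12). No direction is spelled out for items 8 (tobacco) and 9 (alcohol).
- FHNSI: 6 of 10 negative (GP1, GP2, GP4, GE6, H&N3, H&N12).

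Clearly negative items: 7 + 5 + 4 = 16, or 18 if H&N8 and H&N9 count as unfavourable.

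**The plan's own figure.** The total range of 0 to 156 reproduces: 28 + 28 + 24 + 28 + 48 = 4 × 39 = 156. It does so with or without reversal, so a range check would not reveal the omission. The FHNSI range of 0 to 48 does not reproduce, because 4 × 10 = 40. EWB has 6 items, so its maximum is 4 × 6 = 24. FWB has 7 items (0 to 28), but no range is given for it.

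**Formulas.** Let P and N be the numbers of positive and negative items in a score.

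- Sums as written: best state 4P, worst state 4N.
- With reversal: best state 4(P + N), worst state 0.
- A true one-point improvement on every directional item moves the written score by P − N and the reversed score by P + N.

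| Score | P | N | Written, best / worst | Reversed, best / worst | One-point gain, written / reversed |
|---|---|---|---|---|---|
| PWB | 0 | 7 | 0 / 28 | 28 / 0 | −7 / +7 |
| EWB | 1 | 5 | 4 / 20 | 24 / 0 | −4 / +6 |
| FHNSI | 4 | 6 | 16 / 24 | 40 / 0 | −2 / +10 |
| FACT-G | 15 | 12 | 60 / 48 | 108 / 0 | +3 / +27 |
| HNS, items 8–9 held at 0 | 6 | 4 | 24 / 16 | 40 / 0 | +2 / +10 |
| HNS, items 8–9 unfavourable | 6 | 6 | 24 / 24 | 48 / 0 | 0 / +12 |
| Total, items 8–9 held at 0 | 21 | 16 | 84 / 64 | 148 / 0 | +5 / +37 |
| Total, items 8–9 unfavourable | 21 | 18 | 84 / 72 | 156 / 0 | +3 / +39 |

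**Proration does not help.** With n answered items, the reversed PWB is Σ(4 − r) × 7/n = 28 − (Σr × 7/n). The written PWB is therefore exactly 28 minus the intended one, whatever is missing within the allowed limit. Every change from baseline and every between-arm difference keeps its size and changes sign.

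**The total has no stable direction.** If PWB and FWB each truly worsen by 5, the written total changes by +5 − 5 = 0 instead of −10. If only PWB worsens by 5, it changes by +5 instead of −5.

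**Search for a reversal step.** None is found in SAP 5.6.2, SAP 8.7.1, Protocol 10.2.1 or Protocol 11.7.1. The Listing 16.2.9.1.1 shell has only raw and imputed score columns.

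**The case against.** The intent is plain. Both documents say higher is better, both list the FACT manual among their references, and a programmer who knows the instrument would probably reverse the items. A literal sum also contradicts the SAP's own sentence, so quality control could catch it. This lowers the practical risk but does not remove the error. Section 5.6.2 does not send the reader to the manual for scoring; it supplies its own algorithm and instructs the reader to use it. The section is not reliable enough to lean on intent: the HNS line appears twice, and the abbreviations in the formulas (HCS, GFB) do not match the defined ones.

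Three narrower points stand.

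- The SAP calls HNS a 12-item scale, gives it a maximum of 48 and treats higher as favourable for all items. Read literally, that keeps H&N8 and H&N9 in the score and implies that they are reversed.
- The output shells do not match SAP 8.7.1. Tables 15.5.1.1 and 15.5.1.2 cover the total, HNS, individual HNS symptoms and FHNSI, with no table for PWB, EWB or FACT-G. Listing 16.2.9.1.1 is only a mock-up, so the missing reversed column is weak evidence by itself.
- The impact is limited. These analyses are exploratory, the subgroup is run only if the data support it, and the raw answers are kept.

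The duplicate EWB range and the missing FWB range are most simply one slip, with the first EWB meant as FWB.

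**Conclusion.** The concern holds. The scoring rule is wrong as written, and this is more than missing detail. PWB is fully inverted. EWB (4 against 20) and FHNSI (16 against 24) are net inverted. FACT-G keeps only 12 of its 108 points between best and worst health. The total keeps 12 of 156 if the tobacco and alcohol items count as unfavourable, or 20 of 148 if they are held at 0. HNS keeps 0 of 48 or 8 of 40 on the same two readings.

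The counts rest on the item wording in the protocol's sample questionnaire and on the SAP formulas being coded literally. SWB, FWB, the primary PFS test and the main OS and ORR analyses are unaffected. The plan should be corrected before unblinding, because a change of sign made after results are seen would look post hoc.

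**What to change.** In SAP 5.6.2, before the sums, add a step that replaces the response by 4 minus the response for GP1–GP7, GE1, GE3–GE6, H&N2, H&N3, H&N6 and H&N12. State that the reversed values of GP1, GP2, GP4, GE6, H&N3 and H&N12 enter FHNSI.

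State how H&N8 and H&N9 are scored. Reversing both agrees with the SAP's 12-item HNS (0–48) and total (0–156). If they are to be left out, the item count, the proration multiplier and the ranges must change with them (HNS 10 items, 0–40; total 0–148).

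Correct the ranges: PWB, SWB and FWB 0–28; EWB 0–24; FHNSI 0–40. Define FACT-G as PWB + SWB + EWB + FWB, 0–108. Align the abbreviations in the formulas, remove the repeated HNS line, and bring SAP 8.7.1 and the table and figure shells into agreement on which scores are reported. A reversed-score column in Listing 16.2.9.1.1 would make the step visible for checking.

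The cost is one revised SAP section, one derivation step and small changes to the shells. Data collection does not change.

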6. ANALYSIS SETS

6.1. Analysis Sets Definitions

6.1.1. Full Analysis Set

The full analysis set (FAS) will be based on the intent-to-treat principle and will comprise all subjects randomized into the study. Subjects will be analyzed as randomized.

6.1.2. Safety Analysis Set

The safety analysis set includes all subjects who received any amount of study medication. Subjects will be analyzed according to actual treatment received.

6.1.3. Per-Protocol Analysis Set

The per-protocol analysis set will include all subjects in the FAS who have completed at least 1 cycle of treatment, and who were sufficiently compliant with the protocol and without major protocol violation. Full criteria for defining sufficient compliance will be finalized and documented prior to database unblinding.

6.1.4. Pharmacokinetic Analysis Set

The PK analysis set will include all subjects who have received at least 1 dose of study drugs and have evaluable patritumab or cetuximab concentrations.

6.1.5. Patient Reported Outcome Analysis Set

There will be 2 PRO Analysis Sets:

- FACT-H&N Analysis Set
- EQ-5D Analysis Set.

The FACT-H&N Analysis Set will include all subjects in the Full Analysis Set who complete the FACT-H&N assessment at Cycle 1 Day 1, at least partially in a manner that permits imputation of missing responses, according to the approach described in Section 5.6.2.

The EQ-5D Analysis Set will include all subjects in the Full Analysis Set who complete the EQ-5D assessment at Cycle 1 Day 1, at least partially in a manner that permits imputation of missing responses, according to the approach described in Section 5.6.2.

6.2. Protocol Deviations

A list of protocol deviations for the study report will be presented in a data listing.

6.3. Treatment Misallocations

The following rules of reporting efficacy and safety results (eg, under which treatment group) for subjects with errors in treatment allocation will be applied.

If subjects are:

- Randomized but not treated, then they will be reported under their randomized treatment group for efficacy analysis. However, they are by definition excluded from the safety analysis as actual treatment is missing.
- Treated but not randomized, then by definition they will be excluded from the efficacy analyses since randomized treatment is missing, but they will be reported under the treatment they actually received for all safety analyses.
- Randomized but took incorrect treatment, then they will be reported under their randomized treatment group for all efficacy analyses, but will be reported under the treatment they actually received for all safety analyses.

Approved

7. GENERAL STATISTICAL CONSIDERATIONS

This is a multicenter randomized Phase 2 study designed to evaluate the safety and efficacy of patritumab in combination with cetuximab and platinum-based therapy in recurrent/metastatic first-line SCCHN. The primary analyses for this study will occur when at least 53 PFS events have been observed in the HRG high stratum.

At the point of primary analysis for PFS, the treatment assignment for all randomized subjects will be unblinded to designated study personnel for the analysis after data are reconciled and cleaned and a snapshot of the clean database is created. To minimize potential bias, subjects and Investigators will not be informed about individual treatment assignment until study closure.

Final analyses will occur after study closure with mature OS data (i.e., when all subjects have died or a minimum of 13 months after the last subject is randomized whichever comes first). At the time of study closure, subjects who are demonstrating clinical benefit (SD or better) from study treatment may be offered an opportunity to continue study treatment on the extension phase.

Assessments of change from baseline to post baseline or the ratio of post baseline to baseline will include only those subjects with both baseline and post baseline measurements. The last nonmissing value of a variable taken before the first dose of study drug will be used as the baseline value, unless otherwise specified. In general, missing or dropout data will not be imputed for the purpose of data analysis. Descriptive summary statistics (n, mean, median, standard deviation, and range) will be calculated for continuous variables, and for categorical variables, the number and percentage in each category will be displayed by treatment group.

Study Day is calculated as $\langle \text{date} - 1^{\text{st}} \text{ study treatment date} + 1 \rangle$. The date of the first study treatment is Day 1.

7.1. Adjustment for Covariates

No other covariate adjustments will be applied for primary and secondary efficacy analyses, except for the stratification variables if applicable. The PRO analyses will use baseline values of the dependent variable as a covariate in a mixed model.

7.2. Handling of Dropouts or Missing Data

For a description of the handling of censored data for efficacy endpoints such as OS, PFS and TTP, see Section 5.1 above. Imputation of partial or missing AE onset date and concomitant medication date, incomplete tumor assessment dates, and incomplete dates for last contact or death are specified in Section 11.1. The missing data handling for the analyses on patient reported outcomes is described in 5.6.2.1.

7.3. Interim Analyses and Data Monitoring

An independent Data Monitoring Committee (DMC) will be established for this study and will review the ongoing safety of the study participants and monitor the overall

conduct of the clinical trial. The DMC will review accumulating safety data at periodical basis. Based on its ongoing review of the unblinded safety data, the DMC will outline any serious safety concerns and make recommendations to continue, modify, suspend, or terminate the study.

Details on the membership, responsibilities and working procedures of the Independent DMC will be described in the DMC Charter, provided as a separate document in the study file. The same independent Data Analysis Group statistician responsible for providing the safety data will also provide efficacy data (for proper assessment of the risk/benefits of continuing treatment and study) to the DMC for review.

7.4. Multicenter Studies

There will be approximately 35 sites in Europe. Site as a factor will not be formally examined in this study.

7.5. Multiple Comparisons/Multiplicity

This study has only one primary efficacy variable PFS. The testing hypotheses to compare PFS the patritumab arm versus the control arm will be performed in two sequential steps in pre-defined populations (Freidlin 2012 et al). The primary analysis is PFS comparison between the patritumab arm and the control arm in HRG-high stratum of the FAS (Step 1). If the testing in Step 1 is significant, then no further testing will be performed in Step 2 and the 80% confidence intervals of the hazard ratio in HRG low stratum will be estimated. If the testing in Step 1 is not significant, then the testing in FAS (HRG high + low) will be performed in Step 2 (See Section 8.2.1). The results from both steps will be used to guide the decision on future Phase 3 designs. Since this is a proof of concept study, no adjustment for multiplicity will be performed.

